7.8.2 Laboratory data

The analyses of laboratory data will be descriptive in nature and will be based on BI standards "Handling, Display and Analysis of Laboratory Data" [\(11\)](#). Note that data from the central Laboratory will be used for all displays described below, unless otherwise specified.

The analysis of continuous laboratory parameters will be based on normalised values, which means transforming to a standard unit and to a standard reference range. The last assessment before the first randomised treatment prior to the first drug administration at visit 3 is chosen as the baseline value.

Descriptive statistics of laboratory values over time and for the difference from baseline (see [Section 6.7](#)) will be based upon normalised values and provided by visit, including summaries of the last value on treatment, the minimum and maximum value on treatment.

Laboratory values will be compared to their reference ranges; a shift table will be provided for the number of patients within and outside the reference range at baseline and at the last measurement on treatment. This analysis will be based on standardized laboratory values.

Potentially clinically significant abnormalities will be identified based on BI standard rules which are based on converted values and converted reference ranges using SI lab units. These rules will be listed in the SDL appendix of the CTR. Frequency tables will summarise the number of patients with potentially clinically significant abnormalities.

Patients having an abnormal lab value at baseline will be presented separately. A separate listing will present potentially clinically significant abnormal lab values.

All individual laboratory data will be listed. Values outside the reference range will be flagged. In addition, potentially clinically significant values will be flagged in the listing.

To support analyses of liver related adverse drug effects, the frequency of patients with Aspartate Aminotransferase (AST) and/or Alanine Aminotransferase (ALT) $\geq 3x$ upper level of normal (ULN) combined with a total bilirubin $\geq 2xULN$, and the frequency of patients with AST and/or ALT $\geq 10xULN$, will be displayed. This analysis will be based on standardized laboratory values. A graphical analysis of the ALT and total bilirubin values during the on-treatment period will also be performed; the so called eDISH plot. In the graph, for each patient, the peak total bilirubin is presented as a fold increase over the ULN against the peak ALT as a fold increase over the ULN, on a log10 scale. Two reference lines, $2xULN$ for total bilirubin and $3xULN$ for ALT, are drawn onto the graph in order to divide the plane into four quadrants. Normal cases are in the lower left quadrant, potential DILI cases are in the upper right quadrant (Hy's Law quadrant), while the lower right quadrant is known as the Temple's corollary range (ALT $\geq 3xULN$ and total bilirubin $< 2xULN$).

Clinically relevant findings in laboratory data will be reported as baseline conditions (at screening) or as AEs (during the trial) if judged clinically relevant by the investigator, and will be analysed as such.

Results from the pregnancy test will only be listed.

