Risks related to drug-drug interactions (DDI).	See section 1.2	Close monitoring of patients and the prohibited co-administration of impacted drugs such as treatment with a similar mechanism of action [REDACTED]. The use of drugs inhibiting the activity of OATP1B1/3 is restricted. UGT inhibitors/inducers will be restricted. Patients taking drugs that are sensitive CYP3A4 substrates and/or narrow therapeutic index CYP3A4 substrates will be monitored closely. For further guidance, investigators are referred to the Investigator's Brochure, Investigator Site File (ISF) or may contact the sponsor.
Drug-induced liver injury (DILI)	Rare but severe event, thus under constant surveillance by sponsors and regulators.	Timely detection, evaluation, and follow-up of laboratory alterations in selected liver laboratory parameters to ensure patients' safety.
Patient not treated sufficiently due to placebo.	Placebo comparison needed to enable evaluation of effect of BI 685509 on UACR in patients with DKD.	25% of the patients will receive placebo on top of optimal standard of care treatment according to respective local guidelines, which includes either ACEi or ARB treatment

Table 1.4.2: 1 Overview of trial related risks cont.

Investigational Medicinal Product BI 685509		
Possible or known risks of clinical relevance for this trial	Summary of data, rationale for the risk	Mitigation strategy
Patient may be injured by self-collection of blood.	Patients need to take blood from the tip of their finger to allow frequent creatinine measurements for eGFR calculation as a safety marker and exploratory biomarker for kidney function.	A minimally invasive medical device called [REDACTED] kit, to take blood from the tip of their finger. This [REDACTED] tool has been established for easy-to use capillary blood collection at home. Patients will be trained on how to use this. Patients with diabetes are used to glucose determination in blood at home.
Patients may develop AKI or ESRD.	Rare but severe event related to the trial diagnosis. Patients with such an event will need to receive different treatment and are unlikely to benefit from treatment with BI 685509.	Treatment withdrawal criteria include AKI and ESRD as factors to remove the patient from treatment.

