3.3.4.1 Discontinuation of trial treatment

An individual patient will discontinue trial treatment if:

- The patient wants to discontinue trial treatment, without the need to justify the decision.
- The patient has repeatedly shown to be non-compliant with important trial procedures and, in the opinion of both, the investigator and sponsor representative, is not willing or able to adhere to the trial requirements in the future.
- The patient needs to take concomitant medication that interferes with the safety of the investigational medicinal product, refer to [sections 4.2.1](#) and [4.2.2](#). If there is no safety concern then the Sponsor will review on a case-by-case basis as to whether it is appropriate for the patients to continue. This decision will be based on factors such as duration of treatment, dose etc. If the patient needs to modify a dose, where a stable dose is permitted only, this will not automatically require a discontinuation. In this case the sponsor should be consulted.
- The patient develops Acute Kidney Injury as per clinical judgment by the Investigator. The Kidney Disease: Improving Global Outcomes (KDIGO) definition [[R17-2439](#)] should be used for guidance:
 - Increase in serum creatinine by ≥ 0.3 mg/dL (≥ 26.5 $\mu\text{mol/L}$) within 48 hours; or
 - Increase in serum creatinine to ≥ 1.5 times, which is known or presumed to have occurred within the prior 7 days; or
 - Urine volume < 0.5 mL/kg/h for 6 hours.
- The patient progresses to end stage renal disease and needs to obtain renal replacement therapy.
- Patients with a QT or QTcF interval > 500 ms, or an increase of QT or QTcF of > 60 ms from the pre-dose value at Visit 3 (baseline). Such cases must be reported as AEs.
- The patient experiences a severe infection, e.g. with SARS-CoV-2 that precludes their safe participation in the trial, as determined by the investigator.

- The patient can no longer receive trial treatment for any other medical reasons such as surgery, serious or severe Drug Induced Liver Injury (DILI) attributable to the trial drug (see [section 5.2.6.1.4](#)), other adverse events, or other diseases.
- The patient has discontinued trial treatment for at least 10 consecutive days* or has not taken medication at a total of 14 days* during the trial. In case of a temporary reason, trial treatment should be restarted if medically justified, please see [section 4.1.4](#) for dose adjustments. * *a missed day is classed as all 3 doses being missed*

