Regarding AESIs, summaries of AESIs of hypotension and syncope will be presented for both patient-based and event-based analyses. An individual episode of hypotension will be considered as significant or non-significant based on baseline BP and the lowest BP during the episode. Criteria for significant hypotensive episode are:

- For patients with baseline SBP ≤ 140 : decrease $((\text{lowest SBP during the episode} - \text{baseline SBP}) / (\text{baseline SBP})) \geq 30\%$
- For patients with baseline SBP > 140 : decrease $((\text{lowest SBP during the episode} - \text{baseline SBP}) / (\text{baseline SBP})) \geq 40\%$
- Or, lowest SBP during the episode < 90
- For patients with baseline DBP ≤ 70 : $((\text{lowest DBP during the episode} - \text{baseline DBP}) / (\text{baseline DBP})) \geq 30\%$
- For patients with baseline DBP > 70 : $((\text{lowest DBP during the episode} - \text{baseline DBP}) / (\text{baseline SBP})) \geq 40\%$
- Or, lowest DBP during the episode < 50
- Lowest mean arterial pressure (MAP) during the episode < 70

Details of the AESI of Hypotension and Syncope will be also listed.

Category	Safety topic	Definition
AESI	Hypotension	Investigator-reported, as a dedicated AE category on the AE eCRF page
AESI	Syncope	Investigator-reported, as a dedicated AE category on the AE eCRF page

In addition, potential DILI, acute kidney injury, and QT-interval prolongation are defined as follows:

- Potential DILI, defined as: Narrow sub-SMQ ‘Liver related investigations, signs and symptoms’, narrow sub-SMQ ‘Cholestasis and jaundice of hepatic origin’, narrow sub-SMQ ‘Hepatitis, non-infectious’ and narrow sub-SMQ ‘Hepatic failure, fibrosis and cirrhosis and other liver damage-related conditions’, or investigator-reported AESIs.
- Acute kidney injury, defined as: SMQ ‘Acute renal failure’, narrow scope
- QT-interval prolongation, defined as: SMQ ‘Torsade de points/QT prolongation’, narrow scope excluding the PT ‘Syncope’.

Summaries of potential DILI, acute kidney injury, and QT-interval prolongation will be presented for patient-based analyses.

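### No visible SAP display counts patients by creatinine rise from their own baseline: AKI rests on reported AE terms, and the shift table cannot show worsening in patients already above range

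*SAP*

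**What the plan says.** Protocol 1.4.2 lists AKI among the trial risks and describes "frequent creatinine measurements for eGFR calculation as a safety marker". Protocol 3.3.4.1 makes AKI a reason to stop treatment, worded as "The patient develops Acute Kidney Injury as per clinical judgment by the Investigator". It prints the KDIGO criteria as guidance, one of which is "Increase in serum creatinine to ≥ 1.5 times" with a 7-day condition.

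The SAP handles the kidney as follows.

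- **7.8.1:** "Acute kidney injury, defined as: SMQ" Acute renal failure, narrow scope, which works on reported AE terms.
- **7.8.2, AE route:** clinically relevant laboratory findings are reported "as AEs (during the trial) if judged clinically relevant by the investigator, and will be analysed as such".
- **7.8.2, categorical display:** "shift table will be provided for the number of patients within and outside the reference range at baseline and at the last measurement on treatment".
- **7.8.2, continuous display:** "Descriptive statistics of laboratory values over time and for the difference from baseline", by visit, with the last, minimum and maximum on-treatment values.
- **7.8.2, abnormality count:** a frequency table of patients with potentially clinically significant abnormalities. The sponsor-standard rules behind it are said to rest on converted values and converted reference ranges. The section adds: "Patients having an abnormal lab value at baseline will be presented separately".
- **7.8.2, listings:** all individual values, with flags.

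**The concern.** Under SAP 7.4.1 the target dose is chosen on efficacy together with safety, so a patient count of renal deterioration by dose is directly useful. The drug is given on top of an ACEi or ARB to patients with kidney disease, and Protocol 1.2 reports hypotension among the most frequent drug-related AEs in the earlier patient trial.

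The visible count of AKI depends on what investigators report. By Protocol 3.2 they know the dose group, although they are blinded to active drug or placebo within it. Central-laboratory creatinine does not depend on that judgement, but its visible categorical display uses a reference range that some of these patients already exceed at entry, and it looks only at the last value.

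The SAP goes further for other organs. The liver has laboratory-threshold patient counts and a peak-value plot. Hypotensive episodes have percent-from-baseline criteria using the lowest value in the episode. The kidney has no visible equivalent.

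**Working it through.** The plan gives no figure to reproduce. The check asks how often the shift table is blind, and what the other displays supply.

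**Inputs from the documents.** Entry eGFR 20 to <90 (Protocol 3.3.2); the CKD-EPI formula (Protocol 10.2); 60 patients per active dose (Protocol 4.1.3); treatment visits at weeks 2, 4, 6, 12, 18 and 20 (Protocol flow chart).

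**Assumptions, not in the documents.** Upper limit of normal (ULN) for creatinine 1.2 to 1.35 mg/dL in men and 0.95 to 1.1 in women; ages 50 to 75 for step 1 and 55 to 75 for step 2; eGFR normal with the stated mean and SD and then truncated to 20-90, or uniform on 20-90.

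**Step 1: eGFR at which creatinine equals the ULN.** The formula for patients neither Black nor Japanese, above the knot, is:

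- men: 141 × (Scr/0.9)^−1.209 × 0.993^age
- women: 144 × (Scr/0.7)^−1.209 × 0.993^age

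At age 65, 0.993^65 = 0.6334.

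- Man at 1.3 mg/dL: 141 × 0.6411 × 0.6334 = 57.3
- Woman at 1.0 mg/dL: 144 × 0.6497 × 0.6334 = 59.3

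Over all assumed limits and ages the crossing lies at about 51-70 in men and 49-70 in women. A patient below it starts above range.

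**Step 2: share above range at baseline.**

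| Assumed eGFR distribution | Share above ULN |
|---|---|
| mean 40, SD 18 | 65-93% |
| mean 50, SD 20 | 46-82% |
| mean 60, SD 20 | 30-69% |
| uniform 20-90 | 42-68% |

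**Step 3: does a 1.5-fold rise change the shift-table cell?** Age 65, ULN 1.3 (men) and 1.0 (women), values in mg/dL:

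| Baseline eGFR | Man | Woman | Shift table |
|---|---|---|---|
| 25 | 2.58 to 3.87 | 2.04 to 3.06 | outside to outside |
| 40 | 1.75 to 2.62 | 1.38 to 2.08 | outside to outside |
| 55 | 1.34 to 2.02 | 1.06 to 1.60 | outside to outside |
| 70 | 1.10 to 1.65 | 0.87 to 1.31 | within to outside |
| 85 | 0.94 to 1.41 | 0.74 to 1.11 | within to outside |

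Since 1.5^−1.209 = 0.6125, the man at eGFR 40 falls to 40 × 0.6125 = 24.5 without changing cell. In the last two rows the rise is counted only if it persists to the last on-treatment value.

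**Step 4: what the other displays give.**

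| Display | Patient count? | Relative to own baseline? |
|---|---|---|
| AKI search, AE tables | yes, from reported terms | no |
| Shift table | yes, last value only | no, by range |
| Change by visit | no | yes |
| On-treatment maximum | no | not stated |
| Clinically significant abnormalities | yes | rule not visible; described through reference ranges |
| Listings | no | reader must derive it |

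An illustration of why a mean is not a count: if 3 of 60 patients rose from 1.75 to 2.62 and the rest were unchanged, the mean would move by 3 × 0.87 / 60 = 0.04 mg/dL, whereas a count would show 3/60 = 5%.

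**Step 5: timing.** Scheduled visits are 2 to 6 weeks apart, so a peak-to-baseline ratio cannot be tied to the 7-day KDIGO condition.

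**The case against.** A reader might infer that most patients start above range and that a dose-related creatinine rise would therefore go uncounted or unseen. The documents do not support that.

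- **Most is not established.** No reference range or baseline eGFR distribution is given, and the lower ends in step 2 fall below half.
- **A dose-related rise would be visible.** Change from baseline by visit shows a mean shift. The on-treatment maximum captures a rise that later resolves. Every value is listed.
- **Uncounted is not established.** The table of clinically significant abnormalities counts patients, and its creatinine rule sits in a sponsor standard not reproduced here. Patients abnormal at baseline are to be shown separately; the SAP does not say that they are lost.
- **AE capture is wider than the AKI search.** A creatinine rise reported under any preferred term enters the general AE tables.
- **Other sections are blacked out.** Protocol 3.2 plans exploratory use of serum creatinine, so a patient count may exist in text that cannot be read.
- **A ratio over 20 weeks is not AKI.** It mixes acute injury with haemodynamic change and gradual CKD progression.

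All of this stands, and it limits the point to what the visible plan does not count. It does not supply a visible patient count relative to baseline: the summaries give no number of patients, and the abnormality rule is described in terms of reference ranges. The last item governs how the added table must be labelled.

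**Conclusion.** The point holds in a limited form. AKI is counted from reported terms. The shift table cannot show worsening in patients already above range, or a rise that resolved before the last value. No visible SAP display counts patients by rise from their own baseline. The proportion for whom the shift table is blind is roughly 30-90%, resting wholly on the assumed limits, ages and eGFR distributions; the actual case mix would settle it. Safety analysis is descriptive, so nothing here affects the primary or secondary results, sample size, power or alpha. This is a cheap improvement, not an error that invalidates an analysis.

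**What to change.** In SAP 7.8.2 add one descriptive table by randomised dose and placebo (treated set, on-treatment period, central laboratory). It gives the number and percentage of patients whose highest on-treatment creatinine is at least 1.5 times, and at least 2 times, the pre-dose baseline already defined in that section. Cross-tabulate it with the AKI count from 7.8.1, so that rises not reported as AKI are visible by dose. Keep the shift table.

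Label the table *creatinine rise from baseline*, not AKI, and footnote that:

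- visit spacing prevents applying the 7-day KDIGO condition printed in Protocol 3.3.4.1;
- the 2-fold step is an added descriptive cut-off, not taken from the protocol;
- haemodynamic changes and gradual CKD progression are included.

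If a redacted section already gives such a count, a cross-reference in 7.8.2 is enough.

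The cost is one extra table from data already collected, with some non-specific counts. No dose, stopping rule or error rate is touched.

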7.8.3 Vital signs

The analyses of vital signs (SBP, DBP, and pulse rate) will be described by differences of vital signs from baseline (see [Section 6.7](#)) to the EoS visit.

Clinically relevant findings in vital signs data will be reported as baseline conditions (at screening) or as AEs (during the trial) if judged clinically relevant by the investigator, and will be analysed as such.

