5.2.2 Vital signs

Vital signs will be evaluated at the time points specified in the [flow chart](#), prior to the 12-lead ECG and prior to blood sampling as applicable.

This includes systolic and diastolic blood pressure and pulse rate (electronically or by palpation count for 1 minute) in a seated position after 5 minutes of rest. At Visits 3 to 8 vital signs will be measured before dosing and approximately 30 min and 120 min after dosing. BP measurements should be recorded to the nearest 1 mmHg. The results must be included in the source documents available at the site.

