6.2.5 Follow-up period and trial completion

The Follow-up Period consists of three visits, FUp1, FUp2 and FUp3 with a timepoint for UACR and [REDACTED] [REDACTED] in between these visits, please see the [flow chart](#) for timelines and visit details.

The Residual Effect Period (REP) in this study is 7 days, visit FUp1 should therefore be performed no earlier than 7 days after the End of Treatment Visit. FUp visits FUp2 and FUp3 should also be scheduled relative to the EoT Visit, i.e. FUp2 will be 2 weeks after EoT, 3 weeks after EoT there will be home sampling without visit, and FUp 3 should be 4 weeks after EoT.

Visit FUp3 may be conducted as a Home visit where permitted (see [section 6.2.1](#)), however should a patient have any adverse event(s) that require assessment then the Investigator may request they attend the site for a full assessment.

Participation in this trial is concluded once FUp3 has been completed.

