7.2.5 Safety analyses

Adverse events will be coded using the Medical Dictionary for Drug Regulatory Activities (MedDRA). Standard BI summary tables and listings will be produced. All adverse events with an onset between start of treatment and end of the REP, a period of 7 days after the last dose of trial medication, will be assigned to the on-treatment period for evaluation.

All treated patients will be included in the safety analysis. In general, safety analyses will be descriptive in nature and will be based on BI standards. No hypothesis testing is planned.

Statistical analysis and reporting of adverse events will concentrate on treatment-emergent adverse events, i.e. all adverse events that occur between start of treatment and end of the REP. Adverse events that start before first drug intake and deteriorate under treatment will also be considered as 'treatment-emergent'. Adverse events will be summarized by the treatment to which the subject was randomised, and the treatment at the onset of AE for any drug-related AE. In addition, summary of subjects with down-titration due to AE will be provided.

Frequency, severity, and causal relationship of adverse events will be tabulated by system organ class and preferred term after coding according to the current version of (MedDRA) at database lock.

Laboratory data will be analysed both quantitatively as well as qualitatively. The latter will be done via comparison of laboratory data to their reference ranges. Values outside the reference range as well as values defined as clinically relevant will be summarised. Treatment groups will be compared descriptively with regard to distribution parameters as well as with regard to frequency and percentage of patients with abnormal values or clinically relevant abnormal values.

Vital signs, physical examinations, or other safety-relevant data observed at screening, baseline, during the course of the trial and at the end-of-trial evaluation will be assessed with regard to possible changes compared to findings before start of treatment.

Further details will be provided in the TSAP.

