6.7 BASELINE, TIME WINDOWS, AND CALCULATED VISITS

Section 2.2.2 of the CTP:

Throughout this protocol, the term “baseline” refers to the last observation prior to the first intake of trial medication, with the exception of FMV and 10-hour urine UACR. Baseline for the FMV and 10-hour urine UACR, is defined as the mean of all available samples prior to Visit 2 up to and including those prior to the first intake of trial medication. This does not include the UACR measured in spot urine at Screening.

Measurements taken after start of administration of trial treatment will be considered on-treatment values based on the definition in [Section 6.1](#), and will be assigned to visits for statistical analysis, if applicable, as defined below.

Analysis of AE data, potentially clinically significant abnormal laboratory values, concomitant medication, or non-drug therapies, as well as use of rescue therapy will not be based on visits. Therefore, no assignment to time windows will be necessary for such data.

The derivation of the last value, minimum value, and maximum value of laboratory and vital signs data will consider all on-treatment values (whether or not selected in any time window; see [Section 6.1](#) for definition of the on-treatment period) within the period of interest; these will be derived for analysis of laboratory and vital signs data.

All other safety and efficacy measurements will be assigned to visits based on extended time windows around the planned visit dates, defined relative to the day of first trial treatment (which is scheduled for Visit 3).

Repeated and unscheduled efficacy and safety measurements (except for laboratory data) will be handled similarly to scheduled measurements and will also be assigned to a time window depending upon the date of measurement. For handling of laboratory measurements, see also [Section 7.8.2](#).

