8. TIMEPOINT OF RELEASE OF TREATMENT INFORMATION

The treatment information will be released to unblind the trial database after the last patient has completed their EoS/Follow-up visit and all data has been entered and cleaned as defined in the “Data Ready to be Unblinded and/or Final Trial Closure Notification” (RUN) form.

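### SAP 7.8.3 states the vital-sign analysis as change from baseline to the end-of-study visit, literally 28 days after end of treatment, and names no by-visit or post-dose display of the on-treatment readings

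*SAP*

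**What the plan says.** SAP 7.8.3 gives one analysis for systolic pressure, diastolic pressure and pulse rate: they "will be described by differences of vital signs from baseline" "to the EoS visit". It adds only that clinically relevant findings are reported as baseline conditions or adverse events.

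Protocol 5.2.2 sets a dense schedule: "At Visits 3 to 8 vital signs will be measured before dosing and approximately 30 min and 120 min after dosing". The flow chart adds single readings at EoT, FUp2 and FUp3. Protocol 7.2.5 says that vital signs and other safety data observed at screening, at baseline, "during the course of the trial and at the end-of-trial evaluation will be assessed with regard to possible changes". SAP section 4 declares no change to the planned analysis.

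SAP 6.7 assigns safety measurements to visits through windows around the planned visit dates. Repeated and unscheduled readings are likewise "assigned to a time window depending upon the date of measurement". The same section says that last, minimum and maximum values, drawn from all on-treatment readings, will be derived for the analysis of laboratory and vital-sign data.

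**The concern.** The visit named in 7.8.3 is the wrong one for an on-drug effect. A contrast between a pre-treatment baseline and a visit after washout should be near zero in every arm whatever the drug does while it is taken.

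The on-treatment readings matter here. Hypotension, orthostatic dysregulation and tachycardia are in the first row of the protocol's risk table (1.4.2). Protocol 1.2 puts peak plasma concentration at 0.5 to 1.0 hour after a dose, so the 30-minute reading falls at or near the peak. The choice of target dose is to take safety into account (protocol 7.2.2, SAP 7.4.1). A reader who wants the mean change in blood pressure or pulse by dose and time after dosing finds no planned table for it in the visible SAP.

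**Working it through.** **Which visit is EoS?** The protocol has no visit with that label. SAP section 8 times unblinding "after the last patient has completed their EoS/Follow-up visit". Protocol 6.2.5 says "Participation in this trial is concluded once FUp3 has been completed" and "FUp 3 should be 4 weeks after EoT". Together these point to FUp3.

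**How far off drug is it?** Inputs: EoT on Day 141 and FUp3 on Day 169 ± 3 days (flow chart); last dose on the evening before EoT, so Day 140 (protocol 4.1.4); residual effect period 7 days and half-life 9 to 15 hours (protocol 1.2).
- EoT to FUp3: 169 − 141 = 28 days.
- Past the residual effect period: 169 − (140 + 7) = 22 days.
- Half-lives since the last dose, assuming about 12 hours from that dose to the EoT visit: 28 × 24 + 12 = 684 hours; 684/15 = 45.6 and 684/9 = 76.0.
- With the ± 3 day window: 612 to 756 hours; 612/15 = 40.8 and 756/9 = 84.0.

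No drug effect can be expected at that visit on the protocol's own figures.

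**How many readings lack a named by-visit display?** Visits 3 to 8 are 6 visits with 3 readings each: 6 × 3 = 18. Under SAP 6.7 baseline is the last observation before first intake, which is the Visit 3 pre-dose reading, so it does enter the 7.8.3 contrast. That leaves 18 − 1 = 17 per patient: 12 post-dose (6 × 2) and 5 pre-dose (Visits 4 to 8). For 240 patients, 17 × 240 = 4,080. This is an upper limit, because missed visits and early discontinuation reduce it.

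**Side by side with the neighbouring text.**
- SAP 7.8.2 summarises laboratory values over time and by visit, with last, minimum and maximum on treatment. SAP 7.8.3 has no counterpart.
- Protocol 7.2.5 covers changes during the trial as well as at its end. SAP 7.8.3, read literally, covers only the end.
- SAP 6.7 derives on-treatment last, minimum and maximum vital signs. SAP 7.8.3 names no display for them. The last on-treatment value will usually be the EoT reading, taken the morning after the last evening dose, so it is a trough value. The minimum and maximum draw on all post-dose readings but show neither time course nor trough against peak.

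**What if same-day readings were averaged?** The SAP does not say so; this only bounds the consequence. Assume equal effects at 30 and 120 minutes and a pre-dose effect that is a share *s* of the post-dose effect. The mean of the three readings keeps (s + 2)/3: 67% at s = 0, 83% at s = 0.5 and 100% at s = 1. A pre-dose reading alone keeps 0, 50 or 100%. Averaging would dilute the effect, not remove it.

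**The case against.** The strongest reply is that 7.8.3 is terse rather than wrong. Its wording can be read as changes through the EoS visit. The SAP builds on protocol section 7 and declares no change, and the washout-only reading would sit badly with both protocol 7.2.5 and SAP 6.7. That ambiguity is real, but it is a reason to rewrite the sentence, since a programmer could follow either reading.

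A reader might infer that the SAP pools pre-dose and post-dose readings by date. The documents do not support this. SAP 6.7 says nothing about averaging. The date-of-measurement sentence concerns repeated and unscheduled readings, and the reference in 6.7 to values that may or may not be selected in a window suggests selection rather than mixing. The window definitions that 6.7 announces are not in the public text and may settle the matter.

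A reader might also infer that a haemodynamic effect would go unseen. That is too strong:
- On-treatment minimum and maximum values are derived expressly for vital-sign analysis.
- SAP 7.8.1 classes hypotension episodes by lowest systolic, diastolic and mean arterial pressure, with patient-based and event-based summaries.
- Relevant findings become adverse events, and all individual values are listed (SAP section 7).
- The footnote to SAP Table 6.3: 1 mentions further-endpoint analyses of vital signs, in sections that are not public.
- Protocol 1.2 reports no overall relevant blood pressure or heart rate change against placebo over four weeks in earlier work.

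These points stand, and they limit the concern. They do not close it. The hypotension summaries rest on investigator-reported episodes, do not cover pulse rate and cannot show mean shifts by dose. The adverse-event route depends on the judgement of investigators who know the dose group (protocol 3.2). The earlier patient data cover four weeks, against 20 here.

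**Conclusion.** The point holds in a limited form. Read literally, SAP 7.8.3 names a single contrast at a visit 28 days after EoT and 22 days past the residual effect period. It conflicts with protocol 7.2.5 and falls short of what the SAP sets for laboratory data. Up to 17 scheduled on-treatment readings per patient at Visits 3 to 8, or 4,080 in all, have no named by-visit display, and the visible text does not say how pre-dose, 30-minute and 120-minute readings are kept apart.

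This rests on EoS meaning FUp3, on 240 patients with complete visits, and on the public text. Non-public sections may supply part of what is missing. The documents support neither a claim that readings are pooled nor a claim that a blood pressure or heart rate effect would be missed. The primary efficacy analysis is not affected. The change should be made because it gives a better description of a listed risk from data already collected.

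**What to change.** Replace the first sentence of SAP 7.8.3 with: change from the pre-treatment baseline in systolic pressure, diastolic pressure and pulse rate, summarised by dose group and by visit (each on-treatment visit, EoT and follow-up), and shown separately for the pre-dose, 30-minute and 120-minute readings at Visits 3 to 8. At Visit 3 the pre-dose reading serves as the baseline.

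Add to 7.8.3 displays of the on-treatment minimum systolic and diastolic pressure and the on-treatment maximum pulse, which 6.7 already derives.

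State in SAP 6.7 that same-day vital-sign readings are assigned by planned time point as well as by visit. If a non-public section already provides any of this, a cross-reference from 7.8.3 is enough for that part.

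The cost is SAP wording and a few more standard descriptive tables. No new data, visits or hypothesis tests are needed. The change should be made before treatment information is released.
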